10 STATISTICAL METHODS

10.1 Statistical and Analytical Plans

The statistical methods and data presentations for reporting the study will be described in detail in the statistical analysis plan.

Randomization will be central and treatment allocation will be 2:1 (AR101 or placebo). Randomization will be stratified by geographic region (North America, Europe); at least 30% of subjects are planned to be enrolled in Europe.

Data for demographic and baseline characteristics, efficacy, and safety will be summarized by treatment group (AR101 or placebo). Summary statistics will include the mean, number of observations, standard deviation, median, minimum and maximum values for continuous variables, and frequencies and percentages for categorical variables.

Statistical significance is defined as $p < 0.05$ and tests will be 2-sided, unless otherwise specified. CIs will be calculated at the 95% level, reflecting a type I error of 0.05.

Missing values for efficacy variables will not be replaced or imputed; no interpolation or extrapolation will be applied to missing values unless otherwise specified in the statistical analysis plan.

The statistical methods and statistical analysis plan may be affected by a pandemic, epidemic, or other emergency not related to the study as described in [Appendix 3](#).

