10.3 Determination of Sample Size

A sample size of 132 subjects randomly assigned at a ratio of 2:1 to AR101 (88 subjects) or placebo (44 subjects) provides sufficient power to detect a treatment difference for the primary efficacy analysis for each major health authority region (North America and Europe) ([Section 10.5.1](#)).

For North America, the sample size provides 85% power to demonstrate a significantly higher desensitization response rate with AR101 compared with placebo with an at least 15% margin for the primary efficacy endpoint of the proportion of subjects tolerating an at least 600 mg single dose of peanut protein with no more than mild allergy symptoms during the exit DBPCFC. The sample size calculations are based on the Farrington and Manning method ([Farrington, 1990](#)) for the difference in proportions and assume a type I error of 0.05, 2-sided test, a desensitization rate based on the DBPCFC of 55% in AR101-treated subjects, and a maximum desensitization rate of 15% in placebo-treated subjects, conducted in the ITT population.

For Europe, the sample size provides > 95% power to demonstrate a significantly higher desensitization response rate with AR101 compared with placebo for the primary efficacy endpoint of the proportion of subjects tolerating an at least 1000 mg single dose of peanut protein with no more than mild allergy symptoms during the exit DBPCFC. The sample size calculations are based on the Farrington and Manning method for the difference in proportions and assume a type I error of 0.05, 2-sided test, a desensitization rate based on the

DBPCFC of 50% in AR101-treated subjects, and a maximum desensitization rate of 10% in placebo-treated subjects, conducted in the ITT population.

The desensitization rates used in the sample size calculations account for an estimated 25% of subjects across both treatment groups to drop out or discontinue early from the study; these subjects will not be replaced and will be considered nonresponders.

Sample size may be affected by a pandemic, epidemic, or other emergency not related to the study as described in [Appendix 3](#).

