10.5 Analysis of Efficacy

10.5.1 Primary Efficacy Analyses

The primary objective assesses the efficacy of AR101 treatment in peanut-allergic subjects aged 1 to < 4 years.

The primary efficacy endpoints are defined by major health authority region.

- **North America:** The primary efficacy endpoint is the proportion of subjects treated with AR101 compared with placebo who tolerate an at least 600 mg single dose of peanut protein with no more than mild allergy symptoms during the exit DBPCFC.
- **Europe:** The primary efficacy endpoint is the proportion of subjects treated with AR101 compared with placebo who tolerate an at least 1000 mg single dose of peanut protein with no more than mild allergy symptoms during the exit DBPCFC.

The ITT population and Farrington-Manning test will be used for these analyses. Subjects tolerating a single dose of at least 600 mg peanut protein for North America and at least 1000 mg peanut protein for Europe will be considered responders; subjects who do not tolerate a single dose of at least 600 mg peanut protein for North America and at least 1000 mg peanut protein for Europe will be considered nonresponders. Nonresponders will also include subjects who withdraw consent or discontinue early anytime before the exit DBPCFC.

Desensitization response rates and associated 95% CIs will be presented for each treatment group using exact Clopper-Pearson CIs. The 95% CI for the treatment difference (desensitization rate for AR101 treatment minus desensitization rate for placebo) will be based on the Farrington-Manning method. The primary efficacy endpoint for North America will be considered met if the lower bound of the 95% CI is greater than the prespecified margin of 0.15. The primary efficacy endpoint for Europe will be considered met if the lower bound of the 95% CI is greater than 0.

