10.5.2 Secondary Efficacy Analyses

Secondary efficacy endpoints will be assessed in hierarchical order by major health authority region (North America and Europe) if the primary efficacy endpoint analysis is significant at the 0.05 level. Each endpoint will be evaluated for statistical significance (2-sided, $p < 0.05$) only if all preceding in the hierarchy and the primary analysis of the primary efficacy endpoint are statistically significant in favor of AR101. This closed testing procedure maintains the overall type I error rate at 0.05. If any of the preceding tests are not significant, the p-value will be displayed for informational purposes only.

North America:

1. The proportion of subjects who tolerate an at least 300 mg single dose of peanut protein with no more than mild allergy symptoms during the exit DBPCFC will be assessed using the ITT population and Farrington-Manning test. Desensitization response rates and associated 95% CIs will be presented for each treatment group using exact Clopper-Pearson CIs. The 95% CI for the treatment difference (desensitization rate for AR101 treatment minus desensitization rate for placebo) will be based on the Farrington-Manning method.
2. The proportion of subjects who tolerate an at least 1000 mg single dose of peanut protein with no more than mild allergy symptoms during the exit DBPCFC will be assessed using the ITT population and Farrington-Manning test. Desensitization response rates and associated 95% CIs will be presented for each treatment group using exact Clopper-Pearson CIs. The 95% CI for the treatment difference (desensitization rate for AR101 treatment minus desensitization rate for placebo) will be based on the Farrington-Manning method.
3. The maximum severity of allergy symptoms after consuming peanut protein during the exit DBPCFC will be assessed by tabulating the number and percentage of subjects in the ITT population by maximum severity of allergy symptoms at the exit DBPCFC and by treatment group. The Cochran-Mantel-Haenszel statistics with equally spaced scores (row mean score differences statistic) stratified by geographic region will be used to test for a treatment difference.

Europe:

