1. The proportion of subjects who tolerate an at least 600 mg single dose of peanut protein with no more than mild allergy symptoms during the exit DBPCFC will be assessed using the ITT population and Farrington-Manning test. Desensitization response rates and associated 95% CIs will be presented for each treatment group using exact Clopper-Pearson CIs. The 95% CI for the treatment difference (desensitization rate for AR101 treatment minus desensitization rate for placebo) will be based on the Farrington-Manning method.
2. The proportion of subjects who tolerate an at least 300 mg single dose of peanut protein with no more than mild allergy symptoms during the exit DBPCFC will be assessed using the ITT population and Farrington-Manning test. Desensitization response rates and associated 95% CIs will be presented for each treatment group using exact

Clopper-Pearson CIs. The 95% CI for the treatment difference (desensitization rate for AR101 treatment minus desensitization rate for placebo) will be based on the Farrington-Manning method.

3. The maximum severity of allergy symptoms after consuming peanut protein during the exit DBPCFC will be assessed by tabulating the number and percentage of subjects in the ITT population by maximum severity of allergy symptoms at the exit DBPCFC and by treatment group. The Cochran-Mantel-Haenszel statistics with equally spaced scores (row mean score differences statistic) stratified by geographic region will be used to test for a treatment difference.

Full details will be provided in the statistical analysis plan.

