10.7 Analysis of Exploratory Endpoints

Exploratory endpoints will be assessed as follows:

- Change from baseline in peanut-specific and peanut component-specific serum immunoglobulins.
- Change from baseline in mean wheal diameter and mean erythema diameter on SPT to peanut.
- Change from baseline in TRACK and EASI scores.
- Palatability of study treatment, assessed using a palatability survey.
- Proportion of subjects who tolerate a single highest dose of 2000 mg peanut protein (4043 mg cumulative) during the exit DBPCFC.
- Change from baseline in the single highest tolerated dose of peanut protein at the exit DBPCFC.
- Maximum dose of peanut protein reached with no more than mild allergy symptoms at the exit DBPCFC

Full details for these analyses will be provided in the statistical analysis plan.

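### The primary and first two secondary responder tests name no region stratum, although region is the randomisation stratum and the third secondary test uses it: a small efficiency and consistency gap, not a validity error

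*Combined protocol and SAP*

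**What the plan says.** Section 10.1 sets the design: "Randomization will be stratified by geographic region (North America, Europe); at least 30% of subjects are planned to be enrolled in Europe".

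Section 10.5.1 gives the analysis of both primary endpoints: "The ITT population and Farrington-Manning test will be used for these analyses". The interval for the difference between arms is also a Farrington-Manning interval. The North America endpoint "will be considered met if the lower bound of the 95% CI is greater than the prespecified margin of 0.15"; for Europe the bound must exceed 0. No stratum appears in that section.

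Section 10.5.2 treats the first two secondary endpoints in each hierarchy in the same way; each responder proportion "during the exit DBPCFC will be assessed using the ITT population and Farrington-Manning test". For the third, maximum symptom severity, a Cochran-Mantel-Haenszel test is specified and the text reads: "row mean score differences statistic) stratified by geographic region will be used to test for a treatment difference". The section ends: "Full details will be provided in the statistical analysis plan". The material reviewed holds only the protocol's statistical section and no more detailed analysis text, so this point concerns Section 10.5 as written.

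**The concern.** Within each hierarchy the same children pass through one fixed testing sequence. The first three tests name no stratum and the fourth is stratified by region. Nothing in the text explains the change.

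When randomisation is stratified by a factor that predicts response, an analysis that omits the factor has a standard error larger than it needs to be. The result remains valid but is slightly conservative. This matters most for the North America primary endpoint, where planned power is 85% and success depends on a confidence bound clearing 0.15.

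There is also a prespecification issue. Pooled and stratified estimates can differ by a point or more if the arms are not exactly 2:1 within each region. Near the 0.15 bound, that choice could decide the result.

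**Working it through.** **Inputs.** From Section 10.3: 88 AR101 and 44 placebo; two-sided 0.05; 55% against 15% at 600 mg and 50% against 10% at 1000 mg. Dropouts are already counted as nonresponders in these rates. From Section 10.5.1: nulls of 0.15 and 0. From Section 10.1: at least 30% in Europe.

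**Assumptions.** The split is taken as 61/31 in North America and 27/13 in Europe (40/132 = 30.3%), or as 44/22 in each region. Section 10 gives no response rates by region, so gaps of 0, 10 and 20 points (Europe minus North America, the same in both arms) are assumed, with the overall rates held fixed.

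**Step 1: the plan's own power.** Power = Φ[(p1 − p0 − δ − 1.96·s0)/s1]. Here s1² = p1(1−p1)/88 + p0(1−p0)/44, and s0² is the same expression at the restricted maximum-likelihood rates under the null.

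- North America: restricted rates 0.458 and 0.308, s0 = 0.0875, s1 = 0.0756. (0.25 − 1.96 × 0.0875)/0.0756 = 1.04, giving **85.0%** (exact enumeration 85.4%).
- Europe: common null rate (44 + 4.4)/132 = 0.367, s0 = 0.0890, s1 = 0.0699. (0.40 − 1.96 × 0.0890)/0.0699 = 3.23, giving **99.9%**.

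The stated 85% and >95% both reproduce with an unstratified test on all 132 children. With North American children alone (61/31), s0 = 0.1045 and s1 = 0.0904, and power is only about 69%. So both regions enter each test, and region can be used as a stratum.

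**Step 2: the stratified test.** Z = Σ w_j(d_j − δ)/√(Σ w_j² V_j), with w_j proportional to n1j·n0j/Nj. The weights are 61×31/92 = 20.55 and 27×13/40 = 8.78, that is 0.70 and 0.30. V_j uses the restricted rates within region (Farrington-Manning form, FM); the Miettinen-Nurminen form (MN) multiplies V_j by Nj/(Nj − 1). Reject if Z > 1.96, which is equivalent to the lower 95% bound exceeding δ. Every possible outcome was enumerated (62×32×28×14 = 777,728 tables at 30% Europe).

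**Step 3: North America power (%), 55% against 15%, null 0.15.**

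| Europe share | Regional gap | Unstratified | Stratified FM | Stratified MN |
|---|---|---|---|---|
| 30% | 0 | 85.36 | 85.61 | 85.41 |
| 30% | +10 | 85.50 | 85.75 | 85.55 |
| 30% | −10 | 85.50 | 86.47 | 86.15 |
| 30% | +20 | 85.95 | 86.93 | 86.56 |
| 30% | −20 | 85.94 | 88.43 | 88.09 |
| 50% | 0 | 85.36 | 85.58 | 85.38 |
| 50% | ±10 | 85.53 | 86.22 | 85.91 |
| 50% | ±20 | 86.06 | 88.09 | 87.73 |

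The −20 row at 30% Europe implies a European placebo rate of 0.9%, which is extreme. The 0.25-point FM gain with no gap cannot come from region. It reflects the variance form and falls to 0.05 with MN, so the MN column is the better guide to what region contributes.

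The earlier studies in Section 1.2.2 give 600 mg differences (ARC010 minus ARC003) of 68.2 − 67.2 = 1.0 point on AR101 and 9.3 − 4.0 = 5.3 points on placebo. Used as regional gaps, these yield gains of +0.2 (FM) and 0.0 (MN). They are weak proxies: ARC003 was international, and ARC010 had a shorter maintenance period.

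**Step 4: type I error (one-sided, nominal 2.5%).** At 30% against 15% with 30% Europe and gaps of 0, 10 and 20 points, the unstratified test rejects 2.3%, 2.3% and 2.1% of the time. The stratified test stays between 2.2% and 2.4% in either form. At placebo rates of 4–5% with no gap, the unstratified test reaches 2.9% and the stratified test 2.3–2.5%. That excess is small-sample behaviour of the asymptotic test, not a result of omitting region.

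**Step 5: lower placebo rates.** Unstratified power is 97.0% at 55% against 10%, and 97.8% at 55% against 9.3%. At 55% against 10% the gain from stratifying runs from −0.02 to +0.75 points. For the Europe primary endpoint it is at most 0.02.

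**Step 6: how far the two estimates can differ.** With equal regional gaps in both arms, the crude difference is shifted by the gap times (European share of AR101 − European share of placebo).

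| Europe, AR101/placebo | Difference in shares | Shift at 10 points | Shift at 20 points |
|---|---|---|---|
| 27/13 | 27/88 − 13/44 = 0.011 | 0.1 | 0.2 |
| 24/16 | 24/88 − 16/44 = −0.091 | −0.9 | −1.8 |
| 30/10 | 30/88 − 10/44 = 0.114 | 1.1 | 2.3 |

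With exactly 2:1 in each region the shift is zero.

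**The case against.** The strongest reply is that this is a choice between two valid tests. The planned test controls type I error with respect to region, and it matches the method used for the sample size. Where the documents offer any evidence on region, the gain is 0.0 to 0.2 points; gains of 1 to 2.5 need regional gaps that the documents do not support. Section 10.3 assumes "a maximum desensitization rate of 15% in placebo-treated subjects, conducted in the ITT population", so 15% is a ceiling. At the 4.0% placebo rate seen in ARC003 at 600 mg, power is already 99.9%. The third secondary endpoint is an ordinal score analysed by a method that is stratified by construction, so using a different method there is no contradiction. Finally, a common risk difference need not equal the difference between the displayed arm rates, and European placebo would hold only about 13 children.

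Most of this stands as a statement about size: the benefit is modest and may be close to nil. An unstratified test stated as deliberate would be defensible. The objection does not supply a reason in the text for omitting the stratum, and it shows no material loss from including it. The small European placebo group did not take the stratified test above nominal size in the scenarios checked. The mismatch with the displayed rates is real but small unless allocation within a region drifts.

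**Conclusion.** The point holds, as a recommended improvement rather than a required correction. Section 10.5 names no region stratum for the primary and first two secondary responder tests in either hierarchy, while randomisation and the third secondary test use region. The unstratified analysis is valid and the stated power is right.

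The cost of the omission is confined in practice to the North America primary test. At the planned rates and 30% Europe it is 0.05 to 0.25 power points with no regional gap and at most about 2.5 with a 20-point gap; at a 10% placebo rate it is at most 0.75. These figures rest on assumed regional gaps and splits. If a more detailed analysis plan already names the stratum, all that remains is to align Section 10.5 with it.

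**What to change.** For the primary and first two secondary responder endpoints in each hierarchy, specify a region-stratified score test and 95% confidence interval for the common risk difference, with Mantel-Haenszel weights. Keep the nulls of 0.15 and 0 for the primary endpoints, and read the success criterion from that interval. Name one variance form: Farrington-Manning, or Miettinen-Nurminen with the Nj/(Nj − 1) factor in each region. Report the unstratified Farrington-Manning result as a sensitivity analysis, and state that the common difference may not equal the difference between the displayed arm rates.

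The cost is wording in Section 10.5 and the analysis plan plus minor programming. Region is known for every child, so no new data are needed and the sample size does not change. Settle the choice before any treatment assignment is released, because Section 3.3 unblinds children one by one after their exit challenge.

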10.5.2 Secondary Efficacy Analyses

Secondary efficacy endpoints will be assessed in hierarchical order by major health authority region (North America and Europe) if the primary efficacy endpoint analysis is significant at the 0.05 level. Each endpoint will be evaluated for statistical significance (2-sided, $p < 0.05$) only if all preceding in the hierarchy and the primary analysis of the primary efficacy endpoint are statistically significant in favor of AR101. This closed testing procedure maintains the overall type I error rate at 0.05. If any of the preceding tests are not significant, the p-value will be displayed for informational purposes only.

North America:

1. The proportion of subjects who tolerate an at least 300 mg single dose of peanut protein with no more than mild allergy symptoms during the exit DBPCFC will be assessed using the ITT population and Farrington-Manning test. Desensitization response rates and associated 95% CIs will be presented for each treatment group using exact Clopper-Pearson CIs. The 95% CI for the treatment difference (desensitization rate for AR101 treatment minus desensitization rate for placebo) will be based on the Farrington-Manning method.
2. The proportion of subjects who tolerate an at least 1000 mg single dose of peanut protein with no more than mild allergy symptoms during the exit DBPCFC will be assessed using the ITT population and Farrington-Manning test. Desensitization response rates and associated 95% CIs will be presented for each treatment group using exact Clopper-Pearson CIs. The 95% CI for the treatment difference (desensitization rate for AR101 treatment minus desensitization rate for placebo) will be based on the Farrington-Manning method.
3. The maximum severity of allergy symptoms after consuming peanut protein during the exit DBPCFC will be assessed by tabulating the number and percentage of subjects in the ITT population by maximum severity of allergy symptoms at the exit DBPCFC and by treatment group. The Cochran-Mantel-Haenszel statistics with equally spaced scores (row mean score differences statistic) stratified by geographic region will be used to test for a treatment difference.

Europe:

1. The proportion of subjects who tolerate an at least 600 mg single dose of peanut protein with no more than mild allergy symptoms during the exit DBPCFC will be assessed using the ITT population and Farrington-Manning test. Desensitization response rates and associated 95% CIs will be presented for each treatment group using exact Clopper-Pearson CIs. The 95% CI for the treatment difference (desensitization rate for AR101 treatment minus desensitization rate for placebo) will be based on the Farrington-Manning method.
2. The proportion of subjects who tolerate an at least 300 mg single dose of peanut protein with no more than mild allergy symptoms during the exit DBPCFC will be assessed using the ITT population and Farrington-Manning test. Desensitization response rates and associated 95% CIs will be presented for each treatment group using exact

Clopper-Pearson CIs. The 95% CI for the treatment difference (desensitization rate for AR101 treatment minus desensitization rate for placebo) will be based on the Farrington-Manning method.

3. The maximum severity of allergy symptoms after consuming peanut protein during the exit DBPCFC will be assessed by tabulating the number and percentage of subjects in the ITT population by maximum severity of allergy symptoms at the exit DBPCFC and by treatment group. The Cochran-Mantel-Haenszel statistics with equally spaced scores (row mean score differences statistic) stratified by geographic region will be used to test for a treatment difference.

Full details will be provided in the statistical analysis plan.

10.6 Analysis of Safety

All safety analyses will be performed using the safety population. Safety data will be summarized and listed by treatment received.

Safety data will be collected from signed informed consent and assent (where required) through 14 days after the last dose of study product, or through study exit for subjects receiving AR101 treatment in a follow-on study. Safety follow-up data will be collected for at least 30 days after early discontinuation or study exit for subjects with unresolved adverse events, or for at least 6 months after early discontinuation or study exit for subjects with GI adverse events of interest.

Adverse events will be classified by system organ class and coded to preferred term using MedDRA. Adverse events will be classified by severity using the CoFAR grading system for allergic reactions, modified EAACI guidelines for anaphylaxis, and CTCAE for all other adverse events ([Section 8.5](#)).

Summaries of the safety of AR101 and placebo treatment during the study will include the following:

- Overall summary of adverse events
- Incidence of all nonserious and serious adverse events
- Incidence of adverse events by severity grade
- Incidence of adverse events during up-dosing and maintenance
- Incidence and severity of treatment-related adverse events
- Incidence of treatment-related adverse events during up-dosing and maintenance
- Incidence of dose modifications
- Exposure-adjusted event rates for the most frequent adverse events (ie, adverse events in $\geq 5\%$ of the safety population)
- Exposure-adjusted event rates for the most frequent treatment-related adverse events (ie, adverse events in $\geq 5\%$ of the safety population)

- Incidence of early treatment discontinuation due to adverse events and due to chronic or recurrent GI adverse events
- Separate summaries will be presented for anaphylaxis, allergic reaction adverse events, use of epinephrine, and accidental/nonaccidental food allergen exposure

Adverse events with onset before the first dose of study treatment will be listed only.

All medications will be coded using the World Health Organization Drug Dictionary (WHO-DD). Medications will be listed and summarized by Anatomical Therapeutic Chemical (ATC) classification system level 1 and preferred name.

- Prior and concomitant medications, excluding rescue medications, will be summarized separately by ATC class, preferred name, and treatment.
- Rescue medications used during screening, initial dose escalation, up-dosing, maintenance, and overall (including all rescue medications reported on the case report form) will be summarized by ATC class, preferred name, and treatment received.
- All prior, concomitant, and rescue medications will be listed by subject.

Summary statistics will be provided for the TRACK, EASI, and laboratory data if relevant. These data will also be listed by subject.

Full details for the safety analyses will be provided in the statistical analysis plan.

